#### 1.2.4 Study Rationale

The Pipeline™ device has been commercialized in the US since 2011 for the endovascular treatment of adults with large ( $\geq 10 - 24$  mm) or giant ( $\geq 25$  mm) wide-necked IAs in the ICA from the petrous to the superior hypophyseal segments. Over this period of time, additional long-term data has been generated which further confirms the safety and effectiveness of the Pipeline™ device for this indication. Of particular note, long-term data from the PUFs study demonstrate a 0% recurrence rate of occluded aneurysms up to 3-years post-procedure. Additionally, in much geography outside the US, the Pipeline™ device has been approved and commercialized since 2008 for endovascular embolization of cerebral aneurysms.

Although alternative treatment options (surgical clipping or stent-assisted coiling) exist for some small and medium, wide-necked IAs, there remains a need for more effective and durable long-term IA treatments. To that end, the present study aims to evaluate the safety and effectiveness of the Pipeline™ device in unruptured, wide-necked IAs measuring  $\leq 12$  mm (small and medium sized) located in the ICA up to the terminus and the vertebral artery (VA) segment up to and including the posterior inferior cerebellar artery (PICA). The justification for the aneurysm sizes and locations to be included in this study is provided below.

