### 3.3 Additional Data

- Device-related neurologic adverse event rate by 1 year post-procedure
- Modified Rankin Scale (mRS) score at 1 year.
- Aneurysm occlusion at 3 years post-procedure
- Recurrence and retreatment rates at 1, 2 and 3 years post-procedure
- Procedure time
- Radiation exposure (dosage and time)
- Number of Pipeline™ devices utilized

Event-relatedness will be adjudicated by an independent CEC (**Section 8.1**).

The mRS, a validated scoring system for neurologic status after stroke, will be judged by the Investigator and/or staff.

Aneurysm occlusion status will be assessed by an imaging core lab according to the scale of Roy.

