At the investigator’s discretion, the target IA may be retreated at any time during the study. In the event that the target IA is not treated with the Pipeline™ device at the initial scheduled procedure, the subject may be brought in later to undergo the Pipeline™ device placement procedure. In such situations, the date that the subject receives the Pipeline™ device implant will be considered Day 0. Data will be collected for all initial and retreatment procedures.

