### 9.3 Analysis Population

The analysis population will be comprised of the results from 141 treated subjects. Results will be presented based on two populations:

*Intention to Treat* (ITT): defined as all enrolled subjects in whom deployment of the Pipeline™ device was attempted. It is possible that the Pipeline™ device may not reach the target site and the **operator** would not attempt to deploy it, in the rare event that happens, that subject will not be considered part of the ITT population.

*Full Analysis Set* (FAS): defined as a subset of ITT including only those in whom the Pipeline™ device was implanted.

*Per protocol* (PP): defined as all enrolled subjects, had the Pipeline™ device implanted, and were followed without any major protocol deviations.

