### **9.9 Analysis of the Additional Data**

The device-related neurologic adverse event rate at 1 year post-procedure will be tabulated for the ITT population and presented using counts, percentages, and 2-sided 95% exact binomial confidence intervals. The mRS score at 1 year will be dichotomized ( $\geq 2$  vs.  $< 2$ ) and summarized using counts, percentages, and 2-sided 95% exact binomial confidence intervals. Aneurysm occlusion will be tabulated for the Full Analysis Set and presented using counts, percentages, and 2-sided 95% exact binomial confidence intervals. The proportion of subjects who experience recurrence and require retreatment will be summarized using counts, percentages, and 2-sided 95% exact binomial confidence intervals. Procedure time, radiation exposure (dosage and time) and number of Pipeline™ devices utilized will be summarized using descriptive statistics (N, mean, median, standard deviation, minimum and maximum value, and 95% 2-sided confidence limits).

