Modified Rankin Scale (mRS)	Scale for measuring general neurologic function. 0 No symptoms at all 1 No significant disability despite symptoms; able to carry out all usual duties and activities 2 Slight disability; unable to carry out all previous activities, but able to look after own affairs without assistance 3 Moderate disability; requiring some help, but able to walk without assistance 4 Moderately severe disability; unable to walk without assistance and unable to attend to own bodily needs without assistance 5 Severe disability; bedridden, incontinent and requiring constant nursing care and attention 6 Dead
Neck	Width of the opening of the aneurysm where it meets the parent vessel.
Neurological Adverse Event	An adverse event with an underlying neurological cause.
Neurological Death	Subject death due to neurologic reasons.
Per protocol (PP) population	All enrolled subjects, had the Pipeline™ device successfully implanted, and completed the study without any major protocol deviations.
Point of Enrollment	Point at which the subject signs the study Informed Consent Document.
Procedure-related Adverse Event	Event has a strong temporal relationship to the procedure (Day 0).
Procedure time	Start: Time of first Pipeline™ device introduction (i.e., once the Pipeline™ device is advanced into the microcatheter inside the blood stream of the subject.) End: Time of last Pipeline™ device delivery system removal
Retreatment	Any subsequent intervention (post procedure) performed to treat the target IA.
Screen Failure	Screened patient not enrolled in the study.
Serious Adverse Event (SAE)	An adverse event that: a) Led to death, b) Led to serious deterioration in the health of the subject, that either resulted in a. A life-threatening illness or injury, or b. A permanent impairment of a body structure or a body function, or c. In-subject or prolonged hospitalization, or d. Medical or surgical intervention to prevent life-threatening illness or injury or permanent impairment to a body structure or a body function, c) Led to fetal distress, fetal death or a congenital abnormality or birth defect (ISO 14155:2011 3.37)
Serious Adverse Device Effect (SADE)	An adverse device effect that has resulted in any of the consequences characteristic of a serious adverse event. (ISO 14155:2011 3.36)
Small Intracranial Aneurysm	< 7 mm

TERM	DEFINITION

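### As worded, Section 9.9 summarises one joint recurrence-and-retreatment proportion, which can only equal or understate the retreatment rate listed in Section 3.3 and defined in Section 21

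*Combined protocol and SAP*

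**What the plan says.** Section 3.3, and the synopsis in the same terms, lists among the additional data "Recurrence and retreatment rates at 1, 2 and 3 years post-procedure". Section 21 defines retreatment as "Any subsequent intervention (post procedure) performed to treat the target IA", with no condition that the aneurysm first occluded and then recurred. Section 5.4 leaves the decision to the investigator and says that "the target IA may be retreated at any time during the study"; it adds that "Data will be collected for all initial and retreatment procedures".

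The only analysis sentence for this item is in Section 9.9: "The proportion of subjects who experience recurrence and require retreatment will be summarized using counts", with percentages and "2-sided 95% exact binomial confidence intervals". For this item Section 9.9 names neither the analysis population nor the three time points. Recurrence has no entry in Section 21.

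**The concern.** The Section 9.9 sentence describes a single proportion of subjects for whom two things are both true. The listed endpoint is a pair of rates, and the defined term does not depend on recurrence. A programmer who follows Section 9.9 to the letter would count a retreated subject only if recurrence was also recorded.

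The background text uses recurrence for an aneurysm that had first been occluded. Section 1.2.2 does so when describing coil compaction. Section 1.2.4 does so for this device, where long-term data are said to "demonstrate a 0% recurrence rate of occluded aneurysms up to 3-years post-procedure". On that usage, an aneurysm that keeps filling and is then treated again has not recurred, and the subject drops out of the numerator.

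Durability is the stated reason for the study. Sections 1.2.2 and 1.2.4 argue from coiling's recurrence and retreatment rates, and Table 2 gives the two separately. A joint proportion would be comparable with neither column. Beyond 1 year this item is also the only planned summary of retreatment.

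**Working it through.** **No planned figure to reproduce.** The documents state no expected or target retreatment rate, and no sample size or power rests on this item. What follows tests direction and illustrates size.

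**Inputs**
- n = 141, from Section 9.3: "The analysis population will be comprised of the results from 141 treated subjects". It is used for illustration because Section 9.9 names no denominator here.
- Earlier single-arm study of this device (Section 1.2.3): 83 of 95 aneurysms completely occluded at 1 year and no recurrences. Not completely occluded: 95 − 83 = 12, and 12/95 = 12.6%.
- r, the number of subjects retreated: assumed at 4, 8 and 14. These give 2.8%, 5.7% and 9.9% of 141, close to the 3% to 10% range of coiling retreatment rates in Table 2. They are not forecasts.
- f, the share of retreated subjects who also had recurrence: assumed at 0, 0.5 and 1.

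**Formulas**
- Section 21 retreatment rate = r/n.
- Section 9.9 read literally = f·r/n.
- Shortfall = r(1 − f)/n. This is never negative, and with r above 0 it is zero only when f = 1.
- Exact two-sided 95% limits (Clopper-Pearson) for x events: lower = 2.5% point of Beta(x, n − x + 1); upper = 97.5% point of Beta(x + 1, n − x). For x = 0 the upper limit is 1 − 0.025^(1/141) = 2.6%.

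**Results, % (95% interval)**

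| Retreated | Any retreatment (Section 21) | Joint, f = 0 | Joint, f = 0.5 | Joint, f = 1 |
|---|---|---|---|---|
| 4/141 | 2.8 (0.8 to 7.1) | 0.0 (0 to 2.6) | 1.4 (0.2 to 5.0) | 2.8 (0.8 to 7.1) |
| 8/141 | 5.7 (2.5 to 10.9) | 0.0 (0 to 2.6) | 2.8 (0.8 to 7.1) | 5.7 (2.5 to 10.9) |
| 14/141 | 9.9 (5.5 to 16.1) | 0.0 (0 to 2.6) | 5.0 (2.0 to 10.0) | 9.9 (5.5 to 16.1) |

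Over these assumed values the shortfall runs from 0 to 9.9 percentage points. The f = 0 column is what the earlier study's pattern would give: with no recurrences the joint count is zero whatever r is, and the interval carries no information about retreatment.

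**The case against.** The strongest reply is that the sentence is loose shorthand for the two listed rates. The plural in Section 3.3, the unconditional definition in Section 21 and the capture of every retreatment procedure in Section 5.4 all fit that reading, and under it nothing is biased. This stands as a possible reading, so the understatement is conditional on the literal one. It does not remove the need for a change. The literal reading is the natural one for a single proportion, and Section 1.2.4 itself presents retreatment as what follows from major recurrence. Two readings that give different numbers should not be left to the programmer.

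Second, Section 9.5 requires the primary effectiveness outcome to be reached without re-intervention, so retreatment within the first year already counts against the device. That is correct, and it limits the consequence. It does not yield a retreatment rate at 1 year, and it is silent on years 2 and 3.

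Third, the item is descriptive, with no hypothesis or success threshold, and the rate can be recovered from the data. That also stands, and it bears on how serious the point is.

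A reader might be tempted to go further in three ways that the documents do not support:
- **That a joint figure would be set against an all-cause coiling retreatment rate.** Table 2 does not describe its rates as all-cause, and the surrounding text links them to recurrence. Section 1.2.4 (Study Design) plans a historical comparison only in general terms.
- **That persistent filling is the main reason for retreatment after flow diversion.** No section gives reasons for retreatment with this device, and non-occlusion at 1 year is not the same as retreatment.
- **That the shortfall can be sized from the 61% to 65% planning range in Table 8.** That range is for occlusion without significant parent artery stenosis. Its complement includes occluded aneurysms with stenosis, so it does not count non-occluded aneurysms.

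**Conclusion.** The point holds as a defect of wording. Followed literally, Section 9.9 does not estimate the retreatment rate that Section 3.3 lists and Section 21 defines, and its error can only go one way: equal or too low. It would be wrong to say that the protocol has decided to count only retreatments that follow recurrence. It lists a retreatment rate and then describes its analysis in terms that do not match.

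The size cannot be derived from the documents. The contrast of 0/141 with 5.7% needs three things: the literal reading; recurrence meaning loss of an earlier occlusion, which is inferred from usage because the term is undefined; and an assumed 8 retreatments. It also carries over a pattern from an earlier study of aneurysms of at least 10 mm, counted per aneurysm, to subjects with aneurysms of at most 12 mm. The direction depends on none of the assumed counts. No primary conclusion is affected; what is at risk is the reported durability of the treatment. The wording should be corrected before analysis.

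**What to change.** Replace the sentence in Section 9.9 with two separate proportions, each at 1, 2 and 3 years with exact two-sided 95% intervals:

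1. **Retreatment**, as Section 21 defines it and for any reason, among all implanted subjects (the Full Analysis Set).
2. **Recurrence**, with a definition added to Section 21: loss of a complete occlusion previously graded by the core laboratory. Show the number imaged at each time point. Under footnote 7 of Table 5, angiography is optional once the aneurysm is completely occluded at 1 year, so at 2 and 3 years many subjects at risk of recurrence may have no image.

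Retreatment following recurrence can be shown as a subset of the first proportion.

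The cost is a wording change. Section 5.4 already provides for data on every retreatment procedure, so no new collection is needed. The price for the sponsor is that the reported retreatment rate may be less favourable than the joint figure.

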## **9.10 Handling of Missing Data and Deviations**

The number and proportion of subjects eligible will be presented. Subjects who withdraw from the study will be tabulated with the reasons for the withdrawal. For the primary endpoint analyses, the last observed values or conditions will be used for the calculations. Any departure or deviation from these planned statistical methodologies will be documented and discussed in the Statistical Analysis Plan that will include the statistical rationale for divergence.

## **9.11 Safety Analysis**

All analyses regarding subject safety will be predicated on the ITT population. The number and proportion of subjects experiencing each type of event will be summarized overall and by site. Only treatment emergent events will be included in the analysis, i.e., events that began or worsened after enrollment.

The safety of the procedure will be measured by the incidence of adverse events. The following sections describe how the safety endpoints will be analyzed.

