***Subjects are considered enrolled in the study once the subject signs the study Informed Consent Form.***

It is the responsibility of the Investigator to give each subject (or subject's legally authorized representative) prior to inclusion in the study, full and adequate verbal and written information regarding the objective of this study and the confidentiality of the data collected.

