### **5.4 Procedure**

Subjects must undergo the device placement procedure within 60 calendar days of completion of all baseline assessment tests and procedures. The status of the target IA may change between the screening evaluation and the procedure that may change the risk profile of the study procedure.

Therefore, a pre-treatment (baseline) angiogram will be required before the procedure to confirm that the study procedure can be safely carried out and to collect precise images for the core laboratory. If in the unlikely event that the subject is deemed to be ineligible, the subject will not require any study follow-up.

Each subject will undergo a neurologic examination and assessment using NIHSS. The subject will be tested for antiplatelet response (e.g. using VerifyNow (Accumetrics)). Periprocedural heparin per institutional protocol is required. Prior to inserting the study device, the activated clotting time (ACT) should be checked and adjusted as clinically appropriate. Further ACTs will be checked per standard practice.

The physician will place and deploy the appropriate number of Pipeline™ device braids at the target site to treat the IA.

Post-treatment, the investigator will assess device occlusion, placement and overall status of the aneurysm. Angiograms in the anteroposterior (AP), lateral, and working positions will be obtained. The Investigator will take necessary steps to ensure that pre- and post-placement angiograms are performed using similar views, magnifications, and contrast amount to ensure valid “before/after” comparisons. However, these angiographic details will not be collected in case report forms (CRFs). The Investigator will submit procedural angiograms to the imaging core laboratory. The Investigator will ensure that subject identifiers are removed from all submitted images. Image files/CDs should be labeled with the subject’s study ID number.

Medications appropriate for general anesthesia will be administered using standard hospital practice. Platelet inhibition and aggregations status pre- and post-surgical intervention, including antiplatelet antibodies will be evaluated. All medication use during surgery and immediately post-procedure will be documented. Radiation exposure will be recorded as absorbed radiation dose and cumulative fluoroscopy time will be recorded.

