## **6 ADVERSE EVENTS**

The following adverse events will be collected during the course of the study on the eCRFs.

- All Adverse Events (AE) with an underlying neurological cause (Neurological Adverse Events)
- All Device Related Adverse Events
- All Procedure Related Adverse Events
- All Serious Adverse Events (SAE's)

Adverse event status will be evaluated throughout the study. These will include new events occurring after the point of consent in the study until a subject exits the study. Subjects who are enrolled, underwent surgery to implant to study device but did not have the Pipeline™ device implanted for any reason will be followed for 30 days and relevant safety events will be collected. Investigators must obtain all information available to determine the causality and outcome of the AE and to assess whether it meets the criteria for classification as a serious and/or unexpected event requiring notification to the Sponsor, regulatory agency, and as applicable, IRB/EC, within the specified reporting timeframe. AEs will be categorized using the definitions in **Section 6.1**.

All study AEs, as well as the treatment and follow-up required, should be documented in the subject's medical records and in the eCRF. All study AEs will be followed by the Investigator until resolution or until the end of the 3-year follow-up. A list of potential anticipated adverse events is provided in **Section 10.2**.

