### **9.11.2 Missing and Partial Adverse Event Dates**

The start dates for AEs are important for the:

1. Treatment emergent algorithm.
2. The designation of unique AE occurrences.

Completely missing or partially missing adverse event onset dates will be imputed as follows after due diligence to obtain accurate adverse event information has failed.

If the adverse event start date is completely missing then the adverse event will be considered treatment emergent unless it can be determined that the adverse event end date occurred prior to the study procedure. If this is the case, the adverse event will not be considered treatment emergent.

If the adverse event start date is partially missing and the partial date is not sufficient to determine if the event occurred after the study procedure, then the adverse event will be considered treatment emergent unless it can be determined that the adverse event end date occurred prior to the study procedure.

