## **21 DEFINITIONS**

TERM	DEFINITION
Adverse Event (AE)	Any untoward medical occurrence, unintended disease or injury, or untoward clinical signs (including abnormal laboratory findings) in subjects, users or other persons, whether or not related to the investigational medical device. (ISO 14155:2011 3.2)
Adverse Device Effect (ADE)	An adverse event related to the use of an investigational medical device. (ISO 14155:2011 3.1)
Aneurysm Occlusion	According to the scale of Roy: Complete = Complete occlusion, no flow of contrast seen in the aneurysm sac Residual Neck = Partial occlusion, some flow or eddying flow in the aneurysm sac Residual Aneurysm = Incomplete occlusion, apparent flow in the aneurysm sac
Device Migration	Movement of one or more Pipeline™ devices of more than 5 mm in its parent artery location in comparison to the post-placement angiogram
Device-related Adverse Event	Event has a strong temporal relationship to the study device, and alternative etiology is less likely.
Enrolled Ineligible	Enrolled subject who did not meet study eligibility criteria.
Full Analysis Set Population (FAS)	All enrolled subjects including only those in whom the Pipeline™ device was implanted.

TERM	DEFINITION
NIH Stroke Scale (NIHSS)	Tool to quantify neurological impairment caused by stroke 0 No Stroke Symptoms 1-4 Minor Stroke 5-15 Moderate Stroke 16-20 Moderate to Severe Stroke 21-42 Severe Stroke
Procedure	The primary study procedure involving the placement of the Pipeline™ device at Day 0.
Intention to Treat Population (ITT)	All enrolled subjects in whom deployment of the Pipeline™ device was attempted. It is possible that the Pipeline™ device may not reach the target site and the operator would not attempt to deploy it, in the rare event that happens, that subject will not be considered part of the ITT population.
Medium Intracranial Aneurysm	7-12 mm

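### Treatment-emergent status starts at consent in Section 9.11 but at the procedure in Section 9.11.2, so an event that ends before the procedure is classified by how complete its start date is

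*Combined protocol and SAP*

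**What the plan says.** Section 9.11 gives the general rule for the safety tables: "Only treatment emergent events will be included in the analysis, i.e., events that began or worsened after enrollment". The same section bases these tables on the ITT population and says that they measure the safety of the procedure. Section 9.11.3 then bases every AE summary on treatment-emergent events.

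Enrolment has a fixed meaning. Section 5.2 states: "Subjects are considered enrolled in the study once the subject signs the study Informed Consent Form". Section 21 agrees, defining the point of enrolment as: "Point at which the subject signs the study Informed Consent Document".

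Section 9.11.2 covers incomplete onset dates. An event with no start date is "considered treatment emergent unless it can be determined that the adverse event end date occurred prior to the study procedure". The same exception applies to a partial start date when "the partial date is not sufficient to determine if the event occurred after the study procedure". Section 21 defines the procedure as "The primary study procedure involving the placement of the Pipeline™ device at Day 0".

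The interval between the two start points contains reportable events, because Section 6 says of AE collection: "These will include new events occurring after the point of consent in the study until a subject exits the study".

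**The concern.** The plan has two boundaries for one classification. A fully dated event is judged against consent, and an incompletely dated one against the procedure. Which rule applies depends on data quality and not on when the event happened. Two programmers could follow the text and still differ on events in the interval. A late query that supplies a missing date could also move an event into the tables although nothing about the event has changed.

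The consent boundary also sits badly with the stated purpose. Events that began and ended before the procedure cannot have been caused by it. Under the wording of Section 9.11 they nevertheless enter the all-cause AE and SAE rates, including the overall rates with exact 95% confidence intervals in Sections 9.11.5 and 9.11.10.

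**Working it through.** The plan gives no figure to reproduce here. The check sets the rules side by side, traces which outputs they reach, and bounds the length of the disputed interval.

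**1. One event under both rules.** Take an ITT subject who signs consent on day −40 and has a serious AE from day −20 to day −10, with the procedure on day 0 (hypothetical dates).

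- Complete dates: Section 9.11 applies. Onset on day −20 is after consent on day −40, so the event is treatment-emergent.
- Start date missing, end date known: Section 9.11.2 applies. The end on day −10 is before the procedure, so the event is not treatment-emergent.
- Start date partial and insufficient, end date known: Section 9.11.2 again makes it not treatment-emergent.

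The conflict is confined to events that end before the procedure. If the same event had continued past day 0, both rules would count it: Section 9.11 because it began after consent, and Section 9.11.2 because its end does not precede the procedure.

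**2. Which outputs are reached.**

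- *Primary safety endpoint* (Sections 3.1 and 9.4): major stroke in the treated territory or neurological death at 1 year post-procedure. Not affected.
- *Secondary safety endpoints* (Sections 3.2 and 9.7): events at 30 days, and delayed haemorrhage after 30 days, both post-procedure. Not affected.
- *Device- and procedure-related tables* (Sections 9.11.7 and 9.11.8): relatedness under Section 6.1 needs a strong temporal relationship to the device or to the Day 0 procedure, and the CEC adjudicates it. An event that ended before the procedure should rarely qualify. Largely unaffected.
- *30-day AE table* (Section 9.1): defined from the procedure. The consent rule does not lengthen it.
- *All-cause AE and SAE summaries* (Sections 9.11.3 to 9.11.6 and 9.11.10): affected.

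Section 6 narrows this further. Only neurological, device-related, procedure-related and serious AEs are collected, so the events at issue before the procedure are mainly neurological or serious ones. They count only for subjects who later had deployment attempted, because the tables use ITT.

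**3. Length of the disputed interval.** The documents do not state the time from consent to procedure. The nearest statement, in Section 5.4, is: "Subjects must undergo the device placement procedure within 60 calendar days of completion of all baseline assessment tests and procedures". That counts from completion of baseline, not from consent, so 60 days serves here as an assumption and is not a strict cap. Inputs: gap g of 0 to 60 days (assumed), follow-up of 1,095 days (3-year visit), 141 treated subjects (Section 9.2).

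- Share of a subject's observation time: g / (g + 1095). At g = 0 this is 0%. At g = 60 it is 60/1155 = 5.2%.
- Total disputed time: 141 × g. At g = 0 this is 0. At g = 60 it is 141 × 60 = 8,460 subject-days, or 8,460/365.25 = about 23.2 person-years.

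These are shares of time and not of events. The documents give no event rate for the pre-procedure period.

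**The case against.** The best defence is that the consent start is deliberate. It matches AE collection in Section 6, and it errs towards counting more harm. Section 9.11.2 is only a fallback for poor dates and not a second formal definition, and Section 9.1 leaves specific date algorithms to a Statistical Analysis Plan. On this view, aligning Section 9.11.2 to enrolment would cure the mismatch equally well.

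Much of that stands. Counting from consent is a legitimate choice, and Section 9.11.2 is an imputation rule. But such a rule should approximate the classification that complete data would give, and this one applies a different boundary. If consent is intended, Section 9.11.2 needs the change; if the procedure is intended, Section 9.11 does. The text supplied settles neither. Two things favour the procedure: the stated purpose of the tables, and the Synopsis definition of baseline as the last observation before the study procedure, which is the natural reference for an event that worsened.

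A reader might infer more than the documents support:

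- *That the 30-day table covers up to three times its intended exposure*, (60 + 30)/30 = 3. Section 9.1 ties that table to the procedure, so no planned table has such a window.
- *That the interval always contains at least 7 days of dual antiplatelet therapy.* Section 5.3.2 requires 7 days before treatment but does not say that they follow consent. A patient could already be on therapy when consenting.
- *That the primary safety conclusion is at risk.* It is defined post-procedure and does not use the treatment-emergent rule.

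**Conclusion.** The inconsistency is real, and no section reconciles it. An event lying wholly between consent and the procedure is classified in opposite ways according to whether its start date is complete. Section 9.11 read literally also carries pre-procedure neurological and serious events of ITT subjects into the all-cause AE and SAE rates. The consequence is limited to those descriptive tables and is probably small: the disputed window is 0 to about 5.2% of observation time if the consent-to-procedure gap is 0 to 60 days. That range is an assumption, and a longer gap would raise it. This is a minor point, worth correcting because the present text does not give one reproducible count.

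**What to change.** Use one start point in both sections. In Section 9.11, define treatment-emergent events as those that began or worsened on or after the start of the first attempted study procedure, whether or not a device was implanted. In Section 9.11.2, apply the same date when a start date is missing or partial. List events between consent and that procedure separately.

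Day 0 alone would not serve as the anchor. Section 5.4 resets Day 0 to the date of implantation when the aneurysm is not treated at the initial scheduled procedure, so complications of a failed first attempt would fall before Day 0 and drop out. The ITT population in Section 9.3 also includes subjects with an attempted deployment and no implant, who would have no Day 0.

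The cost is a wording change in two places and one extra listing. All-cause AE totals would no longer include pre-procedure events. Collection from consent under Section 6 stays as it is, so no safety data are lost.
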